17.2 PCS Criteria for Vital Signs

Table 14 PCS Criteria for Vital Signs, Weight/BMI, and Waist Circumference

Variable	CDISC Term	Unit	PCS Low	PCS High
Pulse rate, supine/sitting/unknown	PULSE	beats/min	< 50 and decrease ≥ 15	≥ 120 and increase ≥ 15
Diastolic blood pressure, supine/sitting/unknown	DIABP	mmHg	≤ 50 and decrease ≥ 15	≥ 105 and increase ≥ 15
Systolic blood pressure, supine/sitting/unknown	SYSBP	mmHg	≤ 90 and decrease ≥ 20	≥ 180 and increase ≥ 20
Body Temperature	TEMP	°C	decrease ≥ 2	≥ 38.3 and increase ≥ 2

Increase/decrease is relative to the baseline value.

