3.1 Definition of Baseline

For the endpoints based on daily recordings in the eDiary, i.e. the migraine, headache, aura without headache and acute migraine medication endpoints, the baseline values will be based on the data recorded daily in the eDiary during the first 28 days following the screening visit.

For the actigraphy endpoints, the baseline values will be based on the data recorded daily by the wearable device during first 28 days following the screening visit.

For all other endpoints, baseline will be defined as the latest available valid measurement taken prior to the administration of IMP.

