12.3 Vital Sign Measurements

Vital signs including blood pressure, pulse, respiratory rate, and temperate will be summarized based on APTS in Placebo-controlled Period and APTS-OL in Open-label Period by position, visit and treatment group.

Summary of participants with potentially clinically significant vital sign results will also be summarized using the PCS criteria in Appendix 17.2. The number and percentage of participants with at least one potentially clinically significant (PCS) value at any post-baseline assessment time point will be summarized by vital signs, separately for each period. All available assessments in each period will be included in the evaluation of PCS values.

For participants with post-baseline PCS values in the Placebo-controlled Period, listings will be provided including all the values for those participants for the variable prior to entering the

Open-label Period, with flagging of PCS values and out-of-reference-range values. For participants with PCS values occurring after start of Visit 5 IMP infusion, similar listings will be provided including all the values for those participants for the variable. For participants in the APTS-FU set, i.e. for the participants who do not enter the Open-label Period, for example study withdrawals during the Placebo-controlled Period, with PCS values occurring after Week 12, similar listings will be provided including all the values for those participants for the variable.

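### In SAP Table 14 the 38.3 °C limit for high temperature has no effect once baseline is 36.3 °C or above, and the low-temperature cell has no absolute limit

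*SAP*

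**What the plan says.** SAP 17.2, Table 14, sets the PCS criteria for vital signs. For body temperature, in °C, the high criterion is "≥ 38.3 and increase ≥ 2". The low criterion is a fall of at least 2 and nothing else. The footnote reads "Increase/decrease is relative to the baseline value". SAP 3.1 fixes the reference: "For all other endpoints, baseline will be defined as the latest available valid measurement taken prior to the administration of IMP".

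The other rows pair a level with a change in both directions. Pulse is "< 50 and decrease ≥ 15" and "≥ 120 and increase ≥ 15"; diastolic pressure is "≤ 50 and decrease ≥ 15" and "≥ 105 and increase ≥ 15". Systolic pressure has the same form, with 90 and 180 as levels and 20 as the change.

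SAP 12.3 counts participants with at least one post-baseline PCS value and states "All available assessments in each period will be included in the evaluation of PCS values". Its listings cover participants who have a PCS value; they show all of that participant's values for the variable and also mark those outside the reference range. PCS vital-sign changes are a named safety endpoint in both documents.

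**The concern.** In a two-part rule one expects the level to decide at ordinary baselines and the change to act as a guard at unusual ones. In the temperature high cell the order is reversed over part of the ordinary range: the change decides and the printed level is idle. In the low cell there is no level at all, so a normal reading can be flagged as low.

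This matters because Protocol 3.2 deliberately limits safety assessment to adverse events and vital signs including body temperature, and temperature is taken before and after each infusion (SAP Table 13, notes p and q). The PCS count is the part of that assessment that does not depend on investigator judgement. If its temperature row does not operate at the level it states, a post-infusion fever can pass 38.3 °C and appear in neither the PCS count nor, on account of that reading, the PCS listing.

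**Working it through.** The plan states no derived figure on this point, so there is none to reproduce. The check applies the rule as written.

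**Inputs.** The levels and changes come from SAP Table 14 and the baseline from SAP 3.1. The documents give no temperature distribution or normal range, and Protocol 9.4.3 lets each site use its own thermometer. Distributions below are therefore assumptions.

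**High rule.** With baseline B and reading T, the flag needs T ≥ 38.3 and T − B ≥ 2, that is T ≥ max(38.3, B + 2). The level governs only while B + 2 < 38.3, so B < 36.3.

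| Baseline | B + 2 | Working limit | Readings ≥ 38.3 not flagged |
|---|---|---|---|
| 36.0 | 38.0 | 38.3 | none |
| 36.3 | 38.3 | 38.3 | none |
| 36.5 | 38.5 | 38.5 | 38.3 to below 38.5 |
| 36.8 | 38.8 | 38.8 | 38.3 to below 38.8 |
| 37.0 | 39.0 | 39.0 | 38.3 to below 39.0 |

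Example: B = 36.8 and T = 38.7 gives a rise of 1.9. It exceeds 38.3 but is not flagged.

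**Same calculation for the other high cells** (level minus change = the baseline above which the change takes over): pulse 120 − 15 = 105; diastolic 105 − 15 = 90; systolic 180 − 20 = 160. For temperature it is 38.3 − 2 = 36.3.

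**Share of participants with B ≥ 36.3**, assuming a normal distribution, 1 − Φ((36.3 − mean)/SD):

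| Mean | SD 0.3 | SD 0.4 |
|---|---|---|
| 36.0 | 16% | 23% |
| 36.2 | 37% | 40% |
| 36.3 | 50% | 50% |
| 36.5 | 75% | 69% |
| 36.6 | 84% | 77% |
| 36.8 | 95% | 89% |

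For means of 36.5 to 36.8 the range is 69-95%, and the median working limit is mean + 2, or 38.5 to 38.8. For means below 36.3 the share is under half.

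**Low rule.** The flag needs B − T ≥ 2 only.

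- 38.4 to 36.4: fall 2.0, flagged low at an ordinary temperature.
- 38.3 to 36.8: fall 1.5, not flagged.
- Baseline 36.8, rising to 39.0 after infusion, then back to 36.8: the last reading is 0 from baseline and is not flagged low. The 39.0 is flagged high (rise 2.2).

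The first case is possible because the exclusion for out-of-range vital signs (Protocol 5.3, exclusion 18) applies at the Screening Visit, not at the pre-infusion reading.

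**The case against.** The strongest reply is that every high cell requires a level and a change, so the change can override the level in any row: systolic 165 rising to 182 is not flagged either. On that view the temperature row is a matter of calibration, and nothing elsewhere in the documents contradicts it. This is right as far as it goes. What remains is that the override starts at pulse 105, diastolic 90 and systolic 160 but at 36.3 °C for temperature, with no reason given for the difference.

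The second reply is that the information appears elsewhere. Protocol 9.4.3 requires an adverse event for any out-of-range vital sign the investigator judges clinically significant, and SAP 5 and 12.2 give by-visit summaries with minimum and maximum. A false low flag would also be easy to recognise, since the listing shows all of that participant's values. These limit the harm. They do not replace an objective count: the first depends on judgement, and a minimum and maximum do not say how many participants crossed the limit.

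Third, the title of Table 14 also covers weight/BMI and waist circumference, for which no rows appear in the table as read. An entry missing from the low cell cannot be fully excluded, though the other cells look intact.

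Three stronger readings are tempting and not supported:

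- A reader might infer that 38.3 is idle for most participants. That depends on a distribution the documents do not give, and it reverses if baselines centre below 36.3.
- A reader might infer that any resolved fever counts as low. Only one present at the pre-dose baseline and falling by at least 2 °C does.
- A reader might infer that the 2 is an unconverted Fahrenheit change. The unit column says °C, 38.3 °C is 100.94 °F (38.3 × 9/5 + 32), and nothing in the documents mentions Fahrenheit. No replacement value should rest on that guess.

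**Conclusion.** The point holds as a minor defect in a descriptive safety table. Two parts follow from the table alone: the 38.3 °C limit has no effect at any baseline of 36.3 °C or above, and the low-temperature cell is the only one of eight without an absolute limit.

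How often the first matters is uncertain. It affects about 69-95% of participants in the sense that their working limit is set by the rise, if mean baseline is 36.5 to 36.8 °C and the SD 0.3 to 0.4, and under half if the mean is below 36.3 °C. The number who actually have an unflagged reading of 38.3 °C or more will be far smaller and cannot be estimated from the documents. The low-side case is probably rare, since it requires a fever at the reading taken just before infusion.

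**What to change.** Reconcile the temperature row of Table 14 with the other rows, or state why it differs, after checking the low cell against the source table.

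- **High:** let the stated level operate, for example by flagging every post-baseline reading of at least 38.3 °C with any increase from baseline. If the sponsor prefers to leave the row as it is, add a supplementary summary and listing of those readings.
- **Low:** keep the fall of at least 2 °C and also require the value to be below the lower limit of the reference range that SAP 12.3 already uses to mark out-of-range values. The documents do not print that range, so it should be stated or cited in Table 14.

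Under this wording 38.7 from 36.8 is flagged high, and 38.4 falling to 36.4 is not flagged low provided 36.4 lies within the range.

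The cost is one table row and one derivation. A few more participants may be flagged high, while low flags can only become fewer. These are reporting flags: they change no clinical action, efficacy analysis or hypothesis test.

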17.3 Adverse Events of Special Interest

Table 15 Adverse Events of Special Interest

Event types	SMQ/HLT/HLGT	Additional criteria
Cardio/cerebrovascular events	Cardiac arrhythmias (SMQ) (Narrow) Cardiac failure (SMQ) (Narrow) Cardiomyopathy (SMQ) (Narrow) Central nervous system vascular disorders (SMQ) (Narrow) Embolic and thrombotic events (SMQ) (Narrow) Hypertension (SMQ) (Narrow) Ischaemic heart disease (SMQ) (Narrow) Pulmonary hypertension (SMQ) (Narrow) Torsade de pointes/QT prolongation (SMQ) (Narrow)	
Events associated with Suicide	Suicide/self-injury (SMQ) (Narrow)	
Events potentially associated with Trial Drug Infusion	Angioedema and urticaria (HLGT) (primary PTs only) Bronchial disorders (excl neoplasms) (HLGT) (primary PTs only) Infusion site reactions (HLT) (primary PTs only) Oral soft tissue signs and symptoms (HLT) (primary PTs only) Oral soft tissue swelling and oedema (HLT) (primary PTs only) Pruritus NEC (HLT) (primary PTs only) Rashes, eruptions and exanthems NEC (HLT) (primary PTs only) Respiratory disorders NEC (HLGT) (primary PTs only) Respiratory tract signs and symptoms (HLGT) (primary PTs only) Upper respiratory tract disorders (excl infections) (HLGT) (primary PTs only)	TEAE on the day of dosing after the infusion was started or during the 7 days after dosing TEAE on the day of dosing after the infusion was started TEAE on the day of dosing after the infusion was started or during the 7 days after dosing TEAE on the day of dosing after the infusion was started TEAE on the day of dosing after the infusion was started TEAE on the day of dosing after the infusion was started or during the 7 days after dosing TEAE on the day of dosing after the infusion was started or during the 7 days after dosing TEAE on the day of dosing after the infusion was started TEAE on the day of dosing after the infusion was started

Event types	SMQ/HLT/HLGT	Additional criteria
Hepatic events	Drug related hepatic disorders - comprehensive search (SMQ) (Narrow)	
Hypersensitivity and Anaphylactic Reactions	Anaphylactic reaction (SMQ) (Narrow) Angioedema (SMQ) (Narrow) Hypersensitivity (SMQ) (Narrow)	
Seizures	Convulsions (SMQ) (Narrow)	

18 Changes to Analyses Specified in the Protocol

18.1 Definition of Trial Periods

The trial protocol term “safety follow-up period” will not be used when generating the output. Instead, the Open-label Period has been defined to also include collection of data at the Safety-Follow-up visit.

New definition of the Open-label Period: Starts at the beginning of Visit 5 IMP infusion (End of Week 12) and continues up to and including the Safety Follow-up visit (Week 32).

18.2 Objectives and Endpoints

For the primary objective, the following exploratory endpoints have been added:

- Change from baseline in number of days with auras without headache (Weeks 1-4, Weeks 1-12)
- Change from baseline in duration of severe pain (Weeks 1-4, Weeks 1-12)

For the secondary objective to evaluate the efficacy of eptinezumab during the 12-week Open-label Period, the following exploratory endpoints have been added:

- Change from baseline in number of days with auras without headache (Weeks 13-24)
- Change from baseline in duration of severe pain (Weeks 13-24)

For TSQM-9, due to no exposure of IMP prior to Baseline visit, the assessment of overall IMP satisfaction with the TSQM-9 appears to be not relevant to assess at Baseline visit and will be used only as practice. The secondary endpoint is updated to “Treatment Satisfaction Questionnaire for Medication – 9 items (TSQM-9) score at Week 4 and Week 12”.

18.3 Definition of a Migraine Day

For the definition of a migraine day it was clarified that a day with an aura without a headache for which migraine specific treatment was taken, is also considered a migraine day.

For exploratory analyses, two alternative definitions of a migraine day will be applied:

- (1) a day will be qualified as a migraine day based on the symptoms and duration of the headaches occurring on that specific day only

(2) if a headache is lasting several days, all days on which this headache occurs will then be classified as a migraine day if the headache qualifies as a migraine using the approach number 1) for at least one of these days.

18.4 Definition of an eDiary Compliant Day

The definition will not be used.

18.5 Efficacy Analysis

18.5.1 General Efficacy Analysis Methodology

Only descriptive summaries will be presented for the efficacy analyses for the Open-label Period.

18.5.2 Country

Country will be added as a factor also in models for binary endpoints.

18.5.3 MMRM Model

Previous treatment failures-by-month interaction term is added in the MMRM model.

18.5.4 Binary Endpoints

A logistic regression model will be used for all the binary endpoints, except “Migraine on the day after dosing” (in accordance with protocol synopsis, but not protocol body).

18.5.5 Exploratory Endpoints

For analyses of passive registration of movement, “Minutes in no motion (0-10 a.U.)” is used to replace “Minutes in rest period (range 0-300, 101: rest epoch)”.

18.5.6 Subgroup Analyses

Due to a very low number of randomized participants from North America, the subgroup analysis by region (North America and Europe) specified in Section 16.8.9. in the trial protocol, will not be performed.
